9.2. Participants, Recruitment and Criteria of Selection

9.2.1. Participants

The participants of this research will be children with CP GMFCS level III-IV, aged 4 to 12 years and receiving physiotherapy services.

For the sample size ([Annex I](#)), help will be requested from a statistician, and it will depend on factors such as the expected effect size based on previous studies or clinical knowledge, the level of statistical power desired and the level of significance. For example, knowing that similar studies have a sample size of 30, which is always their limitation, a medium effect size is expected, a power of 80% is desired and 0.5 is considered as the level of significance, a sample size of around 64 participants (32 in each group) might be appropriate. However, this sample size might need to be adjusted based on the recruitment rate, dropout rate, and effect size observed during the study.

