9.6. Data Analysis

All data collected from the assessments, questionnaires and the logbook will be analysed using appropriate statistical methods with the help of an expert statistician to achieve the aims of this research protocol. The statistical analyses will be conducted using a statistical software package such as JASP and the statistical significance will be set at p-value <0.05 and CI (Confidence Interval) 95%. When p-value $< 0,05$, the null hypothesis (H_0) will be rejected meaning that the results are statistically significant. The H_0 is: There is no significant difference between the effectiveness of play therapy-based physiotherapy programs and conventional physiotherapy programs in improving treatment adherence and gross motor function in children with cerebral palsy GMFCS level III-IV.

After collecting all data, it will be placed into a spreadsheet for basic data cleaning and categorization ([Annex V](#)). Descriptive statistics (e.g., mean, median, standard deviation, range...) will be calculated to summarize quantitative variables such as age, attendance rate, treatment adherence logbook, GAS score, GMFM-88 score and CP QOL-Child score, while frequency distributions and percentages will be used to summarize categorical variables such as gender, GMFCS level (III or IV), socio-economic status, ethnicity, and type of intervention. All that describes the participants' demographic and baseline characteristics, as well as analyses the distribution of the variables of interest.

Statistical analysis will be done to test the hypothesis using appropriate methodologies based on the data distribution and characteristics. For quantitative variables, t-tests or ANOVA may be used to compare means between the two groups (play therapy-based physiotherapy versus conventional physiotherapy). However, for categorical variables, chi-square or Fisher's exact test might be used, but in this study, it may not be necessary as the hypothesis doesn't include categorical variables.

Moreover, linear regression analysis may be used to investigate the association between treatment adherence and gross motor function while to identify predictors of treatment adherence, gross motor function and quality of life, including age, gender, GMFCS level, social-economic status, ethnicity, and treatment group so potential confounding variables will be controlled for in the

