regression model. In addition, for identifying predictors of treatment adherence each part of the logbook will be analysed in this same way.

Lastly, the findings will be presented concisely and understandably, using tables and graphics and conclusions will be formed based on the statistical significance.

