The applicability and usefulness of this project's outcomes are important for multiple reasons. To begin, cerebral palsy is a chronic disorder that impairs children's ability to move, perform daily tasks and participate in life. Physiotherapy is a significant part of cerebral palsy treatment since it tries to enhance function and minimize secondary complications. When compared to conventional physiotherapy, the use of play-based physiotherapy has been suggested as a potentially more successful strategy to engage children in therapy and promote treatment adherence while improving gross motor function. So, the results of this randomized controlled study will aid in determining if the hypothesis is correct. That's why if the study reveals that is more successful, it might have significant implications for the development of new interventions and treatment protocols for children with CP, which is the main goal of this project.

Furthermore, the identification of potential factors that may influence treatment outcomes is also valuable for improving treatment approaches in the future. By identifying these potential factors, physiotherapists can develop more tailored treatment plans considering the unique needs and circumstances of each patient. All in all, this can help to improve treatment outcomes and ensure that they receive the most effective and tailored physiotherapy program. For example, if this study shows that children from poor socioeconomic status or an specific ethnic group respond better to play therapy-based physiotherapy program or vice versa, physiotherapist may adapt treatment techniques to these specific populations to be more tailored and equitable.

Lastly, in case that the hypothesis is found to be wrong, the methodology of the study, including the inclusion and exclusion criteria and the use of stratified randomization, will add to the domain of cerebral palsy research and serve as a model for future studies as well as the study's emphasis on incorporating individuals from a variety of socioeconomic situations and ethnicities will assist to guarantee that the findings are applicable to a broad range of children with cerebral palsy. Moreover, the study's attention on ethical issues, such as getting informed consent and providing fair access to the study, will contribute to the general ethical standards and best practices in this field.

14. Dissemination Plan

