15.1. Annex I: Calculation of the Sample Size

For calculating the sample size the following formula have been used (F, G):

$$n = \frac{2SD^2(Z_{\alpha/2} + Z_{\beta})^2}{d^2}$$

Where:

- **n** = sample size
- **Z $\alpha/2$** = the Z-score for the desired level of significance so for 95% confidence level $\alpha=0.05$, $Z_{\alpha/2} = 0.05/2 = 0.025$. This from Z table is **1.96**.
- **Z β** = the Z-score for the desired statistical power so for 80% power where β is 0.20, $Z_{\beta} = 0.8416$ from the Z table.
- **SD** = the estimated standard deviation of the outcome variable based on other studies is **2.43** (18).
- **d** = the effect size (difference in means divided by the pooled standard deviation) taking into account the previous study (18) it will be **1.2**.

Having into account all this, the sample size should be:

$$n = \frac{2SD^2(Z_{\alpha/2} + Z_{\beta})^2}{d^2}; n = \frac{2 \times 2.43^2 (1.96 + 0.8416)^2}{1.2^2}; n = 64.37 \approx 64 \text{ participants}$$

Sample size = 64 participants.

Remember that this sample size may need to be adjusted by a statistician based on factors such as recruitment rate and expected dropout rate.

F: Charan J, Biswas T. How to calculate sample size for different study designs in medical research? Indian J Psychol Med. 2013 Apr;35(2):121-6.
G. Kadam P, Bhalerao S. Sample size calculation. Int J Ayurveda Res. 2010 Jan;1(1):55-7.

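### Section 9.6 ties conclusions to statistical significance and gives the 95% CI no role, which invites reading an inconclusive result as evidence against the hypothesis

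*Protocol*

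**What the plan says.** Section 9.6 (Data Analysis) states that "the statistical significance will be set at p-value <0.05 and CI (Confidence Interval) 95"%. When p is below 0.05 the null hypothesis is rejected, "meaning that the results are statistically significant". Nothing is said about p ≥ 0.05. The section closes with the only rule in the protocol for drawing conclusions: "conclusions will be formed based on the statistical significance". No effect estimate, interval criterion or important difference is attached to it.

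Section 13 expects the results to help decide whether the hypothesis is right. It takes up the case where the play-based programme does better, and then the value of the study "in case that the hypothesis is found to be wrong". It describes no inconclusive result.

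Section 9.2.1 and Annex I plan 64 children, 32 per group, with 80% power. Section 9.7 concedes that the sample may be too small, but as a matter of generalisability and not of power.

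**The concern.** A p-value of 0.05 or more does not show that two programmes are equally effective, or that superiority has been ruled out. That depends on which differences the confidence interval excludes. A conclusion formed on significance cannot separate a trial that has ruled out the planned benefit from one too imprecise to say. With nothing in 9.6 on p ≥ 0.05 and no inconclusive outcome in Section 13, a reader of the final report could take a non-significant result as evidence that play-based physiotherapy is no better, when the data were still compatible with the benefit the trial was planned to detect.

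**Working it through.** **Inputs.** From Annex I: SD 2.43, d = 1.2, Z values 1.96 and 0.8416 (two-sided 5%, 80% power). From Section 9.2.1: 64 children, 32 per group. That section also prints "0.5 is considered as the level of significance"; Section 9.6 and Annex I use 0.05, and so does this check.

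**1. The plan's own figure.** n = 2·SD²·(Zα/2 + Zβ)²/d² = 2 × 5.9049 × 7.849 / 1.44 = 64.37. The arithmetic reproduces. However, this formula gives the number per group: 65 after rounding up, or 130 in total. The protocol uses 64 as the total.

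**2. Reading of d.** Annex I defines d as a standardised effect but divides by it in a formula that also contains the SD, so it is used as a raw difference: 1.2/2.43 = 0.494 SD. This agrees with the medium effect expected in Section 9.2.1, if medium means about 0.5 SD (an assumption).

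**3. Power at 32 per arm, one unadjusted t-test, two-sided 0.05.** Noncentrality = 0.494 × √(32/2) = 1.975, against a critical value t(0.975, 62) = 1.999. Power is 49.4% (normal approximation 50.6%). At exactly 0.5 SD it is 50.4%.

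**4. Precision.** Standard error = 2.43 × √(2/32) = 0.6075. Half-width of the 95% CI = 1.999 × 0.6075 = 1.21 units (0.50 SD), against a planning difference of 1.2.

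**5. What a non-significant result can exclude.** It has an estimate between about −1.21 and +1.21. Its interval excludes 1.2 only if the estimate is below about 1.2 − 1.21 = −0.01. Simulating the estimate and its standard error (62 degrees of freedom) gives:

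| True difference | Share of non-significant results whose CI still includes 1.2 |
|---|---|
| 1.2 (planned) | about 95% |
| 0.6 (half) | about 81% |
| 0 | about 50% |

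**6. Sensitivity of the power figure.**
- Baseline adjustment (ANCOVA, named in the abstract) multiplies the SD by √(1 − ρ²). At assumed correlations ρ of 0.3, 0.5 and 0.7, power is about 54%, 63% and 79% (normal approximation). The protocol gives no correlation.
- Assumed dropout of 10% to 20% (no rate is given) lowers the t-test figure to about 45% to 41%.
- If d really were 1.2 SD, power would be 99.7%, but about 11 to 12 per arm would then suffice for 80% power, which does not fit the plan's own result.

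**The case against.** **The rule is not written down.** A reader might infer that the protocol rests conclusions on p < 0.05 alone and treats a non-significant result as proof that the hypothesis is wrong. The documents do not support that. Section 9.6 does not say that significance is the only basis and sets a 95% CI alongside it. Its decision rule covers only p < 0.05. The Section 13 phrase is a remark on the study's usefulness with no criterion attached. The hypothesis is superiority over conventional physiotherapy, so even a negative reading would mean not better, rather than ineffective. This objection stands. What remains is that the text gives no other route to a conclusion and is silent where guidance is needed.

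**The 49% is conditional.** A reader might also infer a 51% chance that a real benefit is declared wrong. That would treat the trial as one unadjusted t-test. There are two primary outcomes and several assessment times, the deciding test is not named, Annex I does not say which outcome has SD 2.43, and ANCOVA could raise power. So 49% describes a single unadjusted comparison, not the error rate of the whole trial. Nor do most non-significant results fail to exclude the planned effect in every case: with no true effect it is about half.

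**The low power belongs elsewhere.** It comes from the per-group number used as the total. Correcting that would bring power to about 80%, but p ≥ 0.05 would still not show the hypothesis to be wrong, so the wording needs attention either way.

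**It could wait for the SAP.** An SAP may refine interpretation, but Section 9.6 already states a basis for conclusions, and that basis is incomplete.

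**Conclusion.** The point holds as a weakness in the stated basis for conclusions, not as an explicit wrong rule. Section 9.6 links conclusions to significance, leaves the interval unused and is silent on p ≥ 0.05; with Section 13, this invites a non-significant result to be read as evidence against the hypothesis.

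Its size: at 32 per arm the interval extends about 1.2 units either side of the estimate, as wide as the planning difference itself. Between about 50% (no effect) and 95% (planned effect real) of non-significant results would leave that difference open. Power for one such comparison is about 49%. These figures assume a single unadjusted t-test, 1.2 as a raw difference, SD 2.43 and no dropout. The point is secondary to the sample-size error in Annex I, which makes inconclusive results more likely.

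**What to change.** - **Section 9.6:** replace the closing sentence on conclusions with: *Conclusions will be based on the between-group difference and its 95% CI; a non-significant result will be reported as inconclusive unless the CI excludes the planning difference of Annex I.* Apply it to the outcome for which that difference was set.
- **Annex I:** name that outcome and state that 1.2 is a raw difference. Separately, correct the use of a per-group number as the total and restate the power for the number actually planned.
- **Section 13:** reword to allow an inconclusive result beside the two cases now described.

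The wording changes are a few sentences and need no extra data or staff. The only downside is that fewer results can be reported as clearly negative: at 32 per arm, only those with an estimate at or below about zero. With 65 per arm the half-width would be about 1.979 × 2.43 × √(2/65) = 0.84, and estimates below about 1.2 − 0.84 = 0.36 would exclude the planning difference.

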9.7. Study limitations

Some potential limitations of the study might include sample size as it may be too small to make generalizable results to a larger population of children with cerebral palsy and the study will only cover children with GMFCS levels III-IV of a specific range of age. So further studies may require a larger sample size.

Secondly, the study may not capture the long-term effects of the interventions, as the follow-up period is relatively short.

Thirdly, owing to the nature of the intervention, participants and physiotherapists will not be able to be blinded to group allocation. This means that there is a risk of bias in the study, as participants and physiotherapists may behave differently or have different expectations based on their group assignment. However, to minimize this risk, outcome assessors will be blinded to group allocation. This means that the assessors who are measuring the outcome of gross motor function will not know which group each participant belongs to so this can help reduce bias in the assessment of outcomes. On the other hand, treatment adherence is partly subjective, and the physiotherapist can be biased. That's why we will provide specific explanation of how to complete the logbook to try to be as much objective as possible.

Fourthly, there can also be external confounding factors such as medication usage, family support or comorbidities, which could influence treatment results. These confounding factors might be avoided or had into account by registering them.

Finally, the use of self-reported quality of life measure completed by parents, guardians, or the participants themselves limits the study. While this measure can give useful information on the child's quality of life, there is a risk of biases, and the subjective nature of the measure may limit the findings' generalisation. Another objective measure of quality of life, might be used in future research.

10. Ethical Considerations

The study will strictly follow ethical guidelines to protect the rights and welfare of the participants. Before the beginning of the study, all subjects will have to provide informed consent signed. Before the informed consent (IC), a full verbal explanation will be done where all questions will be answered. The informed consent ([Annex VI](#)) will include a full explanation of the study's aims, methods, possible risks, and benefits, as well as the confidentiality safeguards that will be put in place. Participants will have the option to withdraw from the research at any moment with no consequences.

The privacy, anonymity and confidentiality of the participants will be rigorously protected. All personal and medical information will be kept strictly secret and only authorized professionals involved in the study will have access to it. Instead of using their names, participants' identities will be secured by providing them unique identification numbers.

Data collected during the study will be analysed and reported in a way that protects the privacy and confidentiality of the participants. Participants and parents or guardians will be able to know the results of the study at any moment.

All potential risks or damage to participants will be minimized. The research therapies are considered to be safe and are widely used in clinical practice. Throughout the study, adverse events will be observed and recorded, and appropriate actions will be taken to manage and report them as needed.

The research will be carried out in accordance with the relevant laws and regulations, as well as ethical guidelines such as the Declaration of Helsinki and Good Clinical Practice. Prior to the start of the study, a corresponding Institutional Review Board (IRB) or an independent ethical committee will examine and approve the study protocol.

11. Workplan

I will use a work plan in the form of a table chronogram (Table 1) to successfully plan and execute this research project. Each task, its timing, and the person responsible will be specified in the table which is separated into the phases of the project. This will make it easier to track progress and guarantee that all components of the project are completed on time. This will be used to increase efficiency and guarantee that the study is done within the timeframe specified while keeping a high level of quality.

The work plan is divided into 4 phases:

- Phase I → During this phase, the project proposal and the research design will be developed. The resources needed for the study will be identified and potential foundation will be looked for. It will end with the approval from the ethical committee and the recruitment of the research team.
- Phase II → During this phase, the recruitment and initial screening will be done. The intervention and the assessment will be carried out and will end with the follow-up assessment.
- Phase III → The analysis and interpretation of the results will be done and the final report will be written.
- Phase IV → Is the last part of the project and it's not time-defined because depending on when the project is finished it will be longer or shorter, but the aim of this phase is to ensure that the study findings are disseminated.

This work plan is just a prediction of how it should be conducted but is subjected to changes based on factors such as recruitment rate, dropout rate and effect size observed during the study. Moreover, there are several people that will be in charge of different tasks, that's why in the Table 2 you can find the description of the role and responsibilities of each member.

Role	Responsibilities
Principal Researcher (PR)	
• Develop the research question and design the research protocol• Obtain funding if necessary

	
 • Supervise research execution and ensure that ethical requirements are followed • Supervise research team and delegate tasks • Analyse study data and interpret results • Write and publish the final report and do the dissemination
Research Assistants (RAs)	
 • Assist the principal researcher with administrative tasks and help tracking study progress • Recruit participants and obtain informed consent • Collect and manage data • Assist with interpretation of results and dissemination of findings
Statistician (ST)	
 • Assists with sample size calculation and randomization • Helps in developing the data analysis plan • Conducts statistical analyses • Assists in the interpretation of statistical findings
Outcome Assessors (OAs)	
 • They will be physiotherapists trained for ensuring that the measures are administrated consistently across all participants • They will not know the participant allocation • Administer and score assessments for gross motor function measure.
Physiotherapists (PTs)	
 • They will be trained on the study protocol and will follow it rigorously • Deliver physiotherapy interventions • Monitor participant progress and adjust interventions as needed • Give parents recommendations • Assess treatment adherence logbook and GAS • Document intervention delivery

Table 2: Roles and responsibilities of research team members.

		Month 0				Month 1				Month 2				Month 3				Month 4				Month 5							
		1	2	3	4	1	2	3	4	1	2	3	4	1	2	3	4	1	2	3	4	1	2	3	4	1	2	3	4
Tasks	Responsible	PHASE I: PLANNING AND PREPARATION OF THE PROJECT																											
Research Question + Hypothesis + Objectives	PR																												
Literature Review + Write Background	PR																												
Study Design + Creation of the protocol	PR																												
Ethics Approval	PR																												
Find Funding Sources	PR																												
Recruitment of the Research Team	PR																												

		Month 4				Month 5				Month 6				Month 7				Month 8				Month 9				Month 10				Month 11				Month 12				Month 13			
		1	2	3	4	1	2	3	4	1	2	3	4	1	2	3	4	1	2	3	4	1	2	3	4	1	2	3	4	1	2	3	4	1	2	3	4	1	2	3	4
Tasks	Responsible	PHASE II: PARTICIPANT RECRUITMENT, INTERVENTION AND ASSESMENT																																							
Recruitment + Screening + IC	RAs + PR																																								
Randomization	PR + ST																																								
Baseline Assesment (week 0)	OAs + RAs																																								
Mid-term Assesment I (week 5)	OAs + RAs																																								
Mid-term Assesment II (week 10)	OAs + RAs																																								
End-Intervention Assesment (week 16)	OAs + RAs																																								
Follow-up Assesment (week 24)	OAs + RAs																																								
Treatment Adherence Assesment	PTs + RAs																																								
Intervention (16 weeks)	PTs																																								

		Month 13				Month 14				Month 15				Month 16			
		1	2	3	4	1	2	3	4	1	2	3	4	1	2	3	4
Tasks	Responsible	PHASE III: DATA ANALYSIS AND REPORT															
Data cleaning + Analysis	PR + ST																
Interpretation of Results	PR + RAs																
Final Report	PR																
	PR + RAs	PHASE IV: DISSEMINATION OF RESULTS															

Table 1: Work plan chronogram. PR: Principal Researcher, RAs: Research Assistants, ST: Statistician, OAs: Outcome Assessors and PTs: Physiotherapists

12. Necessary Resources

